10.3 Primary Efficacy Analysis

The primary efficacy analysis will be conducted among subjects in the ITT population as described in Section 5.1. HCV RNA values and SVR₁₂ will be imputed as described in Section 6.3.

The primary efficacy endpoint is to assess the effect of response to treatment (as assessed by SVR₁₂ status) on clinical outcomes by comparing the time to incidence of the following events between subjects who achieve SVR₁₂ and those who do not.

- All-cause death
- Liver-related death
- Liver decompensation
- Liver transplantation
- Hepatocellular carcinoma
- Composite of any of the above outcomes

For each of the six event types as listed above, a subject's time to event will be defined as the number of days from the first day of study drug to the day the subject experiences an event of interest. All events of interest will be included, regardless of whether the event occurred while the subject was still taking study drug or had previously discontinued study drug. However, events occurred after a subject started another treatment for HCV will be excluded and the subject will be censored at the time of starting the new HCV treatment. If the subject has not experienced an event of interest nor has the subject died (all-cause death), the subject's data will be censored at the date of the subject's last available assessment of clinical outcomes. All-cause death is a censoring event for liver-related death, liver decompensation, liver transplantation and hepatocellular carcinoma. For subjects with no post-baseline assessment, the subject's data will be censored on the first day of study drug. Time to the composite of clinical outcomes is the time to the first occurrence of any clinical outcome.

For each of the six event types, the distribution of time to event will be estimated for subjects who have achieved SVR₁₂ and those who haven't using Kaplan-Meier methodology and compared between the subjects who have achieved SVR₁₂ and those who haven't using the log-rank test.

For each of the six event types, the 1-, 2-, 3-, 4-, and 5-year event-free survival rate will be estimated using Kaplan-Meier methodology and a 95% confidence interval will be constructed separately for those who have achieved SVR₁₂ and those who haven't.

For each of the six event types, a test statistic based on Kaplan-Meier estimates of the event-free survival probability at Year 5 and the estimated variance will be constructed to test the null hypothesis that the 5-year event-free survival rates for subjects who have achieved SVR₁₂ and those who haven't are the same.

For each of the six event types, a Cox proportional hazards (PH) model will be constructed to include all the baseline characteristics as described in Section 7.1, SVR₁₂ status, and other variables as appropriate to compare the risk of experiencing a clinical outcome between subjects who have achieved SVR₁₂ and those who haven't.

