### **Phase 3 Regimen-Controlled Studies: Studies M13-389, M13-961 and M14-002**

Studies M13-389, M13-961, and M14-002 are randomized, regimen-controlled trials that assessed the safety and efficacy of 12 weeks of treatment with 3 DAAs with or without RBV. Studies M13-961 and M14-002 are ribavirin placebo-controlled studies, while Study M13-389 is an open-label study. The patient population was different in each of the 3 studies. Study M13-389 enrolled genotype 1b-infected subjects with prior non-response to pegIFN/RBV, Study M13-961 enrolled genotype 1b-infected subjects who were treatment-naïve, and Study M14-002 enrolled genotype 1a-infected subjects who were treatment-naïve. All three studies excluded subjects with cirrhosis.

In Study M13-389, a total of 186 subjects were randomized and received at least one dose of study drug, of which 34.9% were prior pegIFN/RBV null responders, 28.5% were prior pegIFN/RBV partial responders, and 36.6% were prior pegIFN/RBV relapsers. The

SVR12 rates were 96.6% in the 3-DAA + RBV arm and 100% in the 3-DAA without RBV arm. The difference in SVR12 rates between the 2 regimens met the protocol-specified criteria for noninferiority; hence, the 3-DAA regimen without RBV demonstrated noninferiority compared to 3-DAA + RBV. No subject in either arm experienced on-treatment virologic failure or post-treatment relapse.

In Study M13-961, a total of 419 subjects were randomized and received at least one dose of study drug. The SVR12 rates for treatment-naïve subjects with HCV genotype 1b infection who received either 3 DAAs with or without RBV for 12 weeks were 99.5% and 99.0%, respectively. The difference in SVR12 rates between the 2 regimens in this study also met the protocol-specified criteria for noninferiority. One of the 419 treated subjects (3-DAA + RBV arm) experienced on-treatment virologic failure.

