### **Assessment of Clinical Outcomes**

The following clinical outcomes will be assessed during the study:

- All-cause death: death due to any cause
- Liver-related death: death as the result of a liver-related cause
- Liver decompensation: development of any of the following conditions: ascites, hepatic encephalopathy or variceal bleeding

- Liver transplantation: any subject who had a liver transplantation
- Hepatocellular carcinoma (HCC): development of HCC in any subject at any time during the study. HCC is defined by histologic confirmation or a > 1 cm mass lesion on cross-sectional imaging that meets the diagnostic criteria for HCC according to EASL guidelines.
- Composite of any of the above outcomes

Clinical Outcome events that occur during the Treatment Period through Post-Treatment Week 4 are to be recorded and documented in the eCRF as an AE/SAE (Section 6.0) in addition to being captured in the Clinical Outcome eCRF(s). Clinical Outcome events that occur after Post-Treatment Week 4 are considered a progression of the subject's existing liver disease and are to be recorded in the Clinical Outcome eCRFs only, except when the clinical outcome is death, in which case the AE/SAE eCRF would also need to be completed. This information may be collected over the telephone in the event the subject is unable to return to the investigative site.

An independent outcome committee will review and adjudicate the validity of each clinical outcome.

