4.3 Sample Size

Assuming 4% of subjects do not achieve SVR₁₂ and assuming the 5-year event rate of the composite clinical outcome is 20% in the non-SVR₁₂ subjects, with a 75% reduction in SVR₁₂ subjects (Hazard Ratio of 0.25),^{1,2} then based on two-sample log rank test (using EAST 6.0), a sample size of at least 2000 subjects enrolled in TOPAZ-I (planned to enroll 1650 subjects) and TOPAZ II (planned to enroll 600 subjects) provides greater than 80%

power to reject the null hypothesis of no difference between SVR₁₂ and non-SVR₁₂ subjects in the rate of clinical outcome events. Power calculations were based on a dropout rate of up to 20% for the hazard ratio.

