6.3 Missing Data Imputation

No data will be imputed for any efficacy or safety analyses except for the PRO questionnaires, for analyses of the HCV RNA endpoints, and for analysis of the persistence of resistance. If a respondent answers at least 50% of the items in a multi-item scale of the SF-36v2, the missing items will be imputed with the average score of the answered items in the same scale. In cases where the respondent did not answer at least 50% of the items, the score for that domain will be considered missing. Similarly, the missing items of the FACIT-F questionnaire will be imputed with the average score of the answered items in the same scale as long as more than 50% (≥ 7 out of 13) of the items in the scale are answered. The SF-36v2 Mental and Physical Component Summary measures will not be computed if any domain is missing.

HCV RNA values will be selected for an SVR analysis based on visit windows as defined in Section 6.2. When there is no HCV RNA value in a visit window based on defined visit windows, the closest values before and after the window, regardless of the value chosen for the subsequent and preceding window, will be used for the flanking imputation described below.

If a subject has a missing HCV RNA value at a post-Day 1 visit but with undetectable or unquantifiable HCV RNA levels at both the preceding value and succeeding value, the HCV RNA level will be considered undetectable or unquantifiable, respectively, at this visit for this subject. In addition, if a subject has an unquantifiable HCV RNA level at the preceding value and an undetectable HCV RNA level at the succeeding value, or vice versa, the HCV RNA level will be imputed as unquantifiable at this visit for this subject. For SVR analyses, if there is no value in the appropriate window after flanking imputation but there is an HCV RNA value after the window, then it will be imputed into the SVR window. Subsequent to this flanking and backward imputation, if a subject is missing a value for the visit window associated with the analysis, the subject will be imputed as a visit failure (i.e., not undetectable or unquantifiable).

If a subject starts another treatment for HCV, then all HCV RNA and PRO assessment values for this subject measured on or after the start date of the new HCV treatment will be excluded from analyses. The subject will be considered a failure for summaries of viral response at all time points after the start of the new HCV treatment.

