5. Other (including subjects with documented re-infections and subjects defined as any SVR₁₂ non-responder not meeting the definitions of [1] – [4], such as a subject with a single quantifiable value within the SVR₁₂ window followed by an undetectable value beyond the SVR₁₂ window).

Reasons for SVR₂₄ Non-Response

Subjects who do not achieve SVR₂₄ (SVR₂₄ non-responders) will be categorized as having:

1. On-treatment virologic failure (see **On-treatment virologic failure definition**);
2. Relapse (defined according to the **Relapse₁₂** definition for subjects who complete treatment);
3. Relapsed after achieving SVR₁₂ (see **Relapse₂₄**);
4. Prematurely discontinued study drug with no on-treatment virologic failure (defined as any SVR₂₄ non-responder who prematurely discontinued study drug and did not meet the **On-treatment virologic failure**, **Relapse₁₂**, or **Relapse₂₄** definitions);
5. Missing follow-up data in the SVR₂₄ window [defined as any subject who completed study drug without data in the SVR₂₄ window, and not meeting the definitions of (1), (2), (3), or (4)];
6. Other (including subjects with documented re-infections and subjects defined as any SVR₂₄ non-responder not meeting the definitions of [1] – [5]).

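### The primary outcome comparison pools documented virologic failures with SVR12 non-responders who have none, and no sensitivity analysis separates them

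*SAP*

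**What the plan says.** **Exposure.** For six event types, SAP 10.3 compares subjects with and without SVR12 by Kaplan-Meier curves, log-rank test, a Year 5 test and a Cox model. For the grouping, "HCV RNA values and SVR₁₂ will be imputed as described in Section 6.3".

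**Imputation.** SAP 6.3 works in steps: flanking imputation, then backward imputation from any HCV RNA value after the window, with a local laboratory value as a further substitute. Only when all of these fail does the last rule apply: "if a subject is missing a value for the visit window associated with the analysis, the subject will be imputed as a visit failure".

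**Reasons for non-response.** SAP 10.1 sorts SVR12 non-responders into five categories: on-treatment virologic failure, relapse, premature discontinuation without on-treatment failure, missing data in the window, and Other. Only the first two are documented virologic failure. Relapse12 requires completed treatment. The SAP illustrates Other by a case "such as a subject with a single quantifiable value within the SVR₁₂ window followed by an undetectable value beyond the SVR₁₂ window".

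**Existing sensitivity analyses.** SAP 10.6 defines a population that drops non-responders whose reason is neither on-treatment failure nor relapse. It serves the SVR12 percentage in this study only. SAP 10.3 has no counterpart.

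**Outcome follow-up.** On clinical outcomes the protocol (Assessment of Clinical Outcomes) says: "This information may be collected over the telephone in the event the subject is unable to return to the investigative site". Protocol 5.4.1 adds a yearly contact for survival status, with consent, for subjects who leave the study.

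**Planning figures.** SAP 4.3 starts from "Assuming 4% of subjects do not achieve SVR₁₂" and supposes that "the 5-year event rate of the composite clinical outcome is 20% in the non-SVR₁₂ subjects". It takes a hazard ratio of 0.25, at least 2000 subjects across both studies, and dropout of up to 20%, and states power above 80%.

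**The concern.** Missing = failure is a cautious rule for a response rate. In SAP 10.3 the same rule defines an exposure, and there it has no built-in caution: a cured subject filed as a non-responder brings low-risk person-time into the comparator. The group is small. At 4% of 2000 it holds 80 subjects, with about 14 expected events, so a few labels can change what it represents.

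At stake is how the hazard ratio is read. The objective concerns the effect of virologic response on liver outcomes. If part of the non-SVR12 group reflects missed sampling or early stopping rather than persistent infection, the estimate partly describes attendance. The sponsor accepts this reasoning in SAP 10.6 for the SVR12 percentage but does not carry it to the primary outcome.

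**Working it through.** **1. The plan's power.** Exponential times over 5 years. Non-SVR12 hazard = -ln(0.8)/5 = 0.0446 per year; SVR12 hazard = 0.25 × 0.0446 = 0.0112. Dropout of 20% over 5 years gives a dropout hazard of 0.0446. The event probability is λ/(λ+η) × [1 - exp(-5(λ+η))]: 0.180 for non-SVR12 and 0.0487 for SVR12. Expected events = 80 × 0.180 + 1920 × 0.0487 = 14.4 + 93.5 = 107.9.

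Schoenfeld power = Φ(√(107.9 × 0.04 × 0.96) × ln 4 - 1.96) = Φ(0.86) = 80.6%, which agrees with the plan. Schoenfeld is conservative when the small group has the high hazard; a direct log-rank simulation gives about 98%.

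**2. Who lands in the non-SVR12 group.**

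| Subject | SAP result |
|---|---|
| On-treatment failure or Relapse12, SVR12 not achieved | Non-SVR12, documented failure |
| Empty window, later value below LLOQ, no confirmed earlier rebound | SVR12, by backward imputation |
| No usable value in or after the window | Non-SVR12, by missing = failure |
| Stopped early, not SVR12, no on-treatment failure | Non-SVR12; may or may not be viraemic |
| Single quantifiable value as last in window, later undetectable | Non-SVR12, on an observed value (last-value rule, SAP 6.2; SVR12 definition, SAP 10.1) |

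**3. How large the group without documented failure might be.** The documents do not give this for the present trial. Protocol 3.0 gives Phase 3 SVR12 rates and failure counts; non-SVR12 numbers below are rounded from the percentages.

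| Arm | n | SVR12 % | Non-SVR12 | Virologic failure |
|---|---|---|---|---|
| M11-646 | 473 | 96.2 | 18 | 8 |
| M13-098 | 296 | 96.3 | 11 | 7 |
| M14-002 with RBV | 100 | 97.0 | 3 | 2 |
| M14-002 without RBV | 205 | 90.2 | 20 | 16 |
| M13-099, 12 weeks | 208 | 91.8 | 17 | 13 |
| M13-099, 24 weeks | 172 | 95.9 | 7 | 4 |
| **Arms with derivable n** | | | **76** | **50** |
| M13-389 with RBV | 93 (assumed) | 96.6 | 3 | 0 |
| M13-389 without RBV | 93 (assumed) | 100 | 0 | 0 |
| M13-961 with RBV | 210 (assumed) | 99.5 | 1 | 1 |
| M13-961 without RBV | 209 (assumed) | 99.0 | 2 | 0 |
| **All arms** | | | **82** | **51** |

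Arm sizes in M13-389 and M13-961 are assumed to be about 1:1. For M13-961 the protocol names one on-treatment failure and mentions no relapse, so none is counted. For M13-389 it states: "No subject in either arm experienced on-treatment virologic failure or post-treatment relapse", so every non-responder there lacked virologic failure.

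Share without documented failure: 26/76 = 34%; all arms 31/82 = 38%; without the RBV-free genotype 1a arm, a regimen not used here, 27/62 = 44%.

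**4. Attenuation with full follow-up.** Let a share m of the non-SVR12 group carry the SVR12 hazard, and let the plan's 20% apply to the rest. SVR12 five-year risk = 1 - 0.8^0.25 = 5.4%. Pooled risk = (1 - m) × 20% + m × 5.4%. Observed HR = ln(1 - 0.054)/ln(1 - pooled risk). The last column sets the share m aside, which restores HR 0.25 in a smaller group.

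| m | Pooled risk | HR | Power, pooled | Power, set aside |
|---|---|---|---|---|
| 10% | 18.5% | 0.27 | 75% | 76% |
| 20% | 17.1% | 0.30 | 69% | 71% |
| 30% | 15.6% | 0.33 | 61% | 65% |
| 34% | 15.0% | 0.34 | 57% | 62% |
| 38% | 14.5% | 0.36 | 54% | 60% |
| 44% | 13.6% | 0.38 | 48% | 55% |

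Powers are by Schoenfeld, and the gain is about 1 to 7 points. Simulated power at m = 38% and 44% is 80% and 76% pooled, against 91% and 88% with those subjects set aside.

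**5. Attenuation with early loss.** If the same subjects are censored at about 0.46 year, roughly when the SVR12 visit falls in a 12-week course (24/52), simulation gives HR 0.26 to 0.27 at m = 38% to 44%. Simulated power is then about 88% to 91%, so setting them aside gains essentially nothing.

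**6. The opposite force.** A subject who dies before the SVR12 window also has no value and becomes a failure. With m = 38% and early loss, two such deaths among the 80 move the simulated HR from 0.26 to 0.22, and five move it to 0.17.

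**The case against.** The strongest reply has four parts.

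- **The SAP already protects missing subjects.** A reader might infer that missing = failure turns subjects later found undetectable into non-responders. The documents do not support that. Backward imputation makes a subject with an empty window and a later value below LLOQ a responder, unless rebound was confirmed earlier. The later-undetectable non-responder in SAP 10.1 fails on an observed quantifiable value, not on imputation.
- **Those left missing may contribute little.** They have no usable HCV RNA in or after the window, and many would be censored early. Telephone collection makes longer outcome follow-up possible, but the documents do not say how common it would be.
- **The 34% to 44% is not a misclassification rate.** Some of these Phase 3 subjects may have stopped early and been viraemic, and some may have died. Relapse12 in this SAP likewise leaves out early stoppers who rebound. The share actually cured could be anywhere from zero up to that bound.
- **The planning rate may already allow for the mixture.** SAP 4.3 assigns the 20% to non-SVR12 subjects as a whole. If it describes the pooled group, there is no attenuation from 0.25. The objective is also stated in terms of SVR12 status, so the planned comparison answers it as worded.

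All four stand as limits on size, and the last is a good reason to keep the planned grouping. None removes the structural point: categories that the SAP itself distinguishes are pooled in the primary comparison, and nothing planned shows whether the result depends on that.

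**Conclusion.** The point holds as a gap in the sensitivity analyses, not as an error that invalidates the primary analysis. The non-SVR12 group combines documented virologic failures with subjects who have none, and SAP 10.6 corrects for this only in the SVR12 percentage.

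The attenuation lies between none and an HR of about 0.34 to 0.38. The upper end requires that every Phase 3-type non-responder without documented failure is cured and fully followed, and that the 20% rate applies to viraemic subjects only. With early loss the HR stays at about 0.26 to 0.27.

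A reader might conclude that the hazard ratio is certainly biased toward 1. The documents do not support that either, because deaths before the window enter the same group and act in the other direction. A reader might also want the primary groups rebuilt from the last available HCV RNA. That would use information up to Post-Treatment Week 260, would place an SVR12 subject with late relapse in both groups, and would leave a subject below LLOQ at Post-Treatment Week 4 and missing afterwards in neither.

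**What to change.** In SAP 10.3, keep the planned grouping and add a pre-specified sensitivity analysis of the composite and each component. Fix three groups at the end of the SVR12 window and assign them in this order so that they cannot overlap:

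1. **Responders:** SVR12 by an observed, flanking, backward or local-laboratory value. Later relapse or re-infection does not move them.
2. **Virologic non-responders:** on-treatment virologic failure, Relapse12, or, for early discontinuers, a last HCV RNA value up to the end of the window at or above LLOQ and before any new HCV treatment.
3. **Undetermined:** all others. This includes subjects with no usable value in or after the window, even if below LLOQ earlier, and those with an unconfirmed single quantifiable value later undetectable. Show them as a separate row, listed by SAP reason.

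Compare group 1 with group 2, preferably with follow-up starting at a landmark at the end of the window, which also takes deaths before the window out of the contrast. A backward-imputed value is drawn after the window, so report how many responders rest on one. Leave missing = failure unchanged for the SVR12 percentage.

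Cost: SAP wording and one extra set of tables; most of the categories are already derived. The comparator is smaller and some subjects leave the two-group contrast. The gain is a hazard ratio that can be interpreted; power is a minor argument (about 1 to 7 Schoenfeld points, and essentially none with early loss).

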HCV RNA < LLOQ Analyses for SVR

If a subject is missing an HCV RNA value for the visit window associated with the analysis of SVR after performing the imputations described above, then this value will be imputed with an HCV RNA value from a local laboratory if present; otherwise, the HCV RNA value for this visit will be missing. Subjects with missing HCV RNA data in the analysis window, after imputations, will be imputed as a failure.

HCV RNA Analyses for Relapse and Virologic Failure

If HCV RNA values from the central laboratory are missing but a local laboratory value is present in the appropriate time period, then the local laboratory value will be used to assess post-treatment relapse and on-treatment virologic failure.

Finally, missing sequence data will be imputed as follows in the analysis of the persistence of resistance from the sequences from PT Week 52 through PT Week 260 (5 years). If a signature variant is not detectable by population, clonal or deep sequencing at PT Week 24 (or later), the variant is imputed as not detectable at the PT Week 52 (or timepoints after the sequence with the variant not detectable) and time points thereafter if a sample from Post-Treatment Week 52 or later is not sequenced. If a signature variant is detectable by population, clonal, or deep sequencing at Post-Treatment Week 52 or later, then the variant is imputed as being detectable at earlier time points if the sample at the earlier time point is not sequenced.

7.0 Demographics, Baseline Characteristics, Medical History, and Previous/Concomitant Medications

Demographics, baseline characteristics, medical history, and previous/concomitant medications will be summarized overall and by presence of cirrhosis and genotype 1 subtype on the safety population.

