Breakthrough = confirmed HCV RNA \geq LLOQ after HCV RNA < LLOQ during treatment, or confirmed increase from nadir in HCV RNA (two consecutive HCV RNA measurements > 1 log₁₀ IU/mL above nadir) at any time point during treatment. A single breakthrough value (\geq LLOQ or > 1 log₁₀ IU/mL above nadir) followed by lost to follow-up will be considered a breakthrough (i.e., will not require confirmation).

On-treatment virologic failure = breakthrough or failure to suppress during treatment (all on-treatment values of HCV RNA \geq LLOQ) with at least 6 weeks (defined as study drug duration \geq 36 days) of treatment.

RVR (rapid virologic response) = HCV RNA < LLOQ in the Week 4 window.

EOTR (end of treatment response) = HCV RNA < LLOQ in the Week 12 window for subjects receiving 12 weeks of treatment and in the Week 24 window for subjects receiving 24 weeks of treatment.

SVR₄ = HCV RNA < LLOQ in the SVR₄ window (4 weeks after the last actual dose of study drug) without any confirmed quantifiable (\geq LLOQ) post-treatment value during that SVR window.

SVR₁₂ = HCV RNA < LLOQ in the SVR₁₂ window (12 weeks after the last actual dose of study drug) without any confirmed quantifiable (\geq LLOQ) post-treatment value before or during that SVR window.

SVR₂₄ = HCV RNA < LLOQ in the SVR₂₄ window (24 weeks after the last actual dose of study drug) without any confirmed quantifiable (\geq LLOQ) post-treatment value before or during that SVR window.

Relapse₁₂ = confirmed HCV RNA \geq LLOQ between end of treatment and 12 weeks after last actual dose of active study drug (up to and including the SVR₁₂ assessment time point) for a subject with HCV RNA < LLOQ at Final Treatment Visit who completes treatment.

Relapse₂₄ = confirmed HCV RNA \geq LLOQ during SVR₂₄ window among subjects who achieved SVR₁₂ and have data available during the SVR₂₄ window.

Relapse_{late} = confirmed HCV RNA \geq LLOQ at any time after the SVR₂₄ assessment time point for a subject who achieved SVR₂₄ and has post-SVR₂₄ HCV RNA data available.

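### SAP 10.3 starts the clock at first dose but groups by SVR12, so any death before the SVR12 window counts as a non-SVR12 death, biasing all-cause death and the composite toward SVR12

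*SAP*

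**What the plan says.** SAP 10.3 sets the time origin for all six event types: "a subject's time to event will be defined as the number of days from the first day of study drug". It adds: "All events of interest will be included, regardless of whether the event occurred while the subject was still taking study drug". The population is every dosed subject in both studies (SAP 5.1.1), so survival to the SVR12 assessment is not required. The SVR12 and non-SVR12 groups are compared by Kaplan-Meier curves, log-rank, "a test statistic based on Kaplan-Meier estimates of the event-free survival probability at Year 5", and a covariate-adjusted Cox model.

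SVR12 is assessed "12 weeks after the last actual dose of study drug", with a window of Study Drug End Day 57 to 126 (SAP 6.2, Table 3). SAP 6.3 can fill an empty window by flanking values, or from a later sample ("if there is no value in the appropriate window after flanking imputation but there is an HCV RNA value after the window"), or from a local laboratory. Otherwise, "Subjects with missing HCV RNA data in the analysis window, after imputations, will be imputed as a failure".

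For the other endpoints, "All-cause death is a censoring event for liver-related death, liver decompensation, liver transplantation and hepatocellular carcinoma". Protocol 5.3.2.1 describes the primary endpoint as events in the post-treatment period, which differs from SAP 10.3. Neither document contains a landmark, delayed entry or a time-dependent SVR12 term. The sensitivity analyses in SAP 10.6 concern the SVR12 rate only.

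**The concern.** Group membership depends on something learned months after the clock starts. For a 12-week completer the window opens at Study Day 84 + 57 = 141; for a 24-week completer, at 168 + 57 = 225; for early stoppers, sooner. A subject who dies before then has no sample in or after the window, so neither flanking nor backward imputation can apply and the subject is a failure. SVR12 subjects cannot die in that interval, while every death in it falls on the comparator. This is immortal-time bias.

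It matters because the comparator is small. The plan expects 4% without SVR12, about 80 of 2000. With no true effect they would have only about 4 composite events over the study, so one or two deaths placed there by definition are a large share. The hazard ratio by SVR12 status is the study's main product, and all-cause death is one of its named outcomes.

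**Working it through.** **1. The plan's own power.** SAP 4.3 gives 4% non-SVR12, a 20% five-year composite rate in them, hazard ratio 0.25, 20% dropout, and at least 2000 subjects (1650 + 600 planned).

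- Non-SVR12 hazard: −ln(0.8)/5 = 0.0446 per year. SVR12 hazard: one quarter, 0.0112. Dropout hazard: 0.0446.
- Events = n·λ/(λ+γ)·(1 − e^(−5(λ+γ))): 80 × 0.5 × 0.36 = 14.4, plus 1920 × 0.2 × 0.243 = 93.5, total 107.9.
- Schoenfeld: Φ(√(107.9 × 0.04 × 0.96) × ln 4 − 1.96) = Φ(0.86) = 80.5%.

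This reproduces the stated figure of more than 80%. At 2250 subjects it is 121.4 events and 84.9%.

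**2. How many early deaths?** There are two indirect estimates.

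- Phase 3 (protocol Table 2): 1 death among 770 + 401 + 509 + 208 + 172 = 2060 actively treated subjects. Assuming about 114 days of observation, 1 × (2000/2060) × (141/114) = 1.2, exact Poisson limits 0.03 to 6.7.
- The plan's rates: the pooled composite rate is 0.04 × 20% + 0.96 × 5% = 5.6%. At constant hazard over 1904 days (84 + 1820), 2000 × (1 − e^(−140h)) with h = −ln(0.944)/1904 gives 8.5 composite events before Study Day 141. If 10%, 25% or 50% of these are deaths (assumed), that is 0.8, 2.1 or 4.2. There may be fewer, since entry excludes decompensation and HCC.

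**3. Effect with no true difference.** Simulation: 2000 subjects, 4% non-SVR12 at random, exponential events, 20% dropout, 17% on 24 weeks (assumed), and k early deaths on Study Days 1-140 assigned to non-SVR12. False benefit means z beyond 1.96 in favour of SVR12. Ranges are across repeated simulations.

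| Early deaths k | Log-rank, composite | Log-rank, all-cause death (3% at 5 years, assumed) | Year-5 test, composite |
|---|---|---|---|
| 0 | about 3-4% | about 4% | 0.7% |
| 1 | about 7-8% | about 11% | 1.6% |
| 2 | about 15-16% | about 24% | 3.3% |
| 4 | about 46% | 71-76% | 13.3% |

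The median composite hazard ratio moves from 1.04 to 0.83 with one early death and 0.69 with two. The zero-death row exceeds the nominal 2.5% because the groups are so unequal; the bias is the excess over that row. With all-cause death at 2% to 4% instead of 3%, one death gives 10-14% and two give 21-34%.

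**4. Effect if the plan is right.** With a true hazard ratio of 0.25, the estimate is 0.25, 0.24, 0.22 and 0.20 for k = 0, 1, 2 and 4.

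**5. Landmark.** Starting at Study Drug End Day 126 (Study Day 84 + 126 = 210 or 168 + 126 = 294) holds composite false benefit at about 3-4% and all-cause death at about 4%, whatever k is. Classification must use only HCV RNA available by then. If 2-5% of SVR12 subjects lack a window sample (assumed) and are classified from a later one, all-cause-death false benefit is 4.4-7.7% instead of 4.0%.

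**6. Power of the landmark.** With a 4% comparator, 2000 subjects give 93-94 events and 75%; 2250 give 105-106 events and 79-80%.

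**The case against.** At the only document-based estimate, about one early death, the effect is modest. Composite false benefit rises by about 4 points, the Year-5 test stays below its nominal 2.5%, and a true hazard ratio of 0.25 would move only to 0.24. The four-death row rests on an assumed 50% death share, although four lies inside the Phase 3 limits. All of this stands, and it bounds the concern.

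The protocol names Cox regression, which the SAP adjusts for baseline covariates; that adjusted model was not simulated. This is a real limit on the stated sizes. It does not remove the bias, because misclassification arises from survival after baseline.

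Early dropouts without HCV RNA also become non-SVR12, without an event. Including them lowered composite false benefit slightly: from 8.2% to 7.1% with one death and from 16.8% to 14.7% with two.

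A reader might infer that all six outcomes are biased this way. The documents do not support that: a survivor with early HCC, decompensation or transplantation can still provide a sample and be classed either way. A reader might also infer that the landmark must replace the first-dose ITT analysis throughout. That would discard early events from endpoints this mechanism does not bias, and would change the primary population without need.

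**Conclusion.** The rule as written builds immortal time into all-cause death and the composite, in favour of SVR12. Liver-related death is affected only through early liver-related deaths, because other deaths are censored there; the documents give no basis for a size. Log-rank and unadjusted Cox are affected most, the Year-5 test much less.

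The bias matters if the true effect is small or absent, and for the size of benefit reported. It would be wrong to infer that a finding of benefit is necessarily an artefact: at the planned hazard ratio the conclusion survives even four early deaths. The mechanism and direction follow from the text. The sizes rest on an unknown early-death count, constant hazards, an assumed 3% death rate, and about 80 non-SVR12 subjects. This should be fixed before the final analysis.

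**What to change.** In SAP 10.3, for all-cause death, liver-related death and the composite:

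- Add a landmark analysis starting at Study Drug End Day 126, among subjects alive, in follow-up and free of the event being analysed on that day.
- Classify SVR12 only from central or local HCV RNA available by the landmark. Keep missing-equals-failure for subjects still in follow-up, so the comparator stays near 4%.
- List earlier events by type and SVR12 status.
- Report the landmark result beside the first-dose ITT result, and base any claim of SVR12 benefit on death or the composite on the landmark result.

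Leave decompensation, transplantation and HCC as planned. Reconcile the event period in protocol 5.3.2.1 with SAP 10.3; restricting to post-treatment events alone would still leave post-treatment days 1-56 biased.

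No new data are needed. The cost is that events in about the first 7 months (12-week treatment) or 10 months (24-week treatment) leave the landmark comparison. With a 4% comparator, Schoenfeld power falls from about 80% to 75% at 2000 subjects and from about 85% to 79-80% at 2250; simulated log-rank power is 96% and 97.5% with the landmark, against 98% and 99% from first dose.

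State which comparator is used. If subjects without HCV RNA were removed from it, the non-SVR12 share could be about 2.5% (Phase 3 virologic failures: 8 + 7 + 0 + 1 + 18 + 17 = 51 of 2060). Schoenfeld power could then fall to about 54% at 2000 and 58-59% at 2250 (simulated log-rank 87% and 89%).
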